2004). In addition, the regular supervised prescription regimen may by itself help the patient to structure his daily life. Oral application of sustained release dexamphetamine, with a much slower onset and limited peak effect than crack-cocaine, clearly meets the rationale for substitution treatment. As in any medication study, the primary focus of our study will be on the balance between (potential) benefit and harm produced by the medication, taking into consideration the personal and societal damage associated with continued illicit use of cocaine, in a situation without effective pharmacological treatment options.

STUDY OBJECTIVE

The overall objective of this feasibility study is to investigate the usefulness of sustained release dexamphetamine in the treatment of cocaine dependence, and – dependent upon the results of both this study and the parallel studies of topiramate and modafinil (see Preface) – to yield one or more candidate medications for future investigation in a large-scale confirmatory controlled trial. Specifically, the study aims to evaluate, in crack dependent patients with comorbid heroin dependence, the response to medically prescribed oral dexamphetamine SR (60 mg/day) as an add-on to heroin-assisted treatment, in terms of potential efficacy, acceptance, compliance, safety, and patient satisfaction.

GENERAL STUDY DESIGN

The study will be conducted using a multicenter, double-blind, placebo-controlled, randomized treatment design. Following screening and baseline assessment, eligible patients in a heroin-assisted maintenance treatment program will be randomly allocated (ratio: 1:1) by the collaborating pharmacist to (continued) heroin-assisted treatment plus 12 weeks treatment with placebo (control group; n=36) or to (continued) heroin-assisted treatment plus 12 weeks treatment with sustained release dexamphetamine 60 mg/day (experimental group; n=36). Randomization will be concealed, using a computer-generated randomization list, and will be prestratified by treatment center (4 treatment centers). Study assessments will take place at baseline, and 4, 8, and 12 weeks after baseline. The primary time point at which treatment outcome will be determined is 12 weeks after baseline.

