STUDY MEDICATIONS

Safety profile

Sustained release dexamphetamine sulfate

For the purpose of the present study, sustained release dexamphetamine sulfate tablets of 30 mg each were manufactured by the Slotervaart pharmacist (group of [name]), in compliance with the principles and guidelines of good manufacturing practice (see appendix: IMP-dossier, July 2013).

In the United States, sustained release dexamphetamine sulfate is marketed under the brand name Dexedrine® (Spansule capsules), for the treatment of ADHD and narcolepsy. The study medication in the present trial contains the same active ingredient – dexamphetamine sulfate, prescribed in sustained release form – and has a similar dissolution profile as Dexedrine® (see appendix: IMP-dossier, July 2013). The Medication Guide for Dexedrine® (see link below) summarizes the following possible side effects (adverse reactions) for sustained release dexamphetamine sulfate:

Cardiovascular:	Palpitations, tachycardia, elevation of blood pressure. There have been isolated reports of cardiomyopathy associated with chronic amphetamine use.
Central nervous system:	Psychotic episodes at recommended doses (rare), overstimulation, restlessness, dizziness, insomnia, euphoria, dyskinesia, dysphoria, tremor, headache, exacerbation of motor and phonic tics, and Tourette's syndrome.
Gastrointestinal:	Dryness of the mouth, unpleasant taste, diarrhea, constipation, other gastrointestinal disturbances. Anorexia and weight loss may occur as undesirable effects.
Allergic:	Urticaria.
Endocrine:	Impotence, changes in libido.

Source: <http://dailymed.nlm.nih.gov/dailymed/lookup.cfm?setid=18b7c145-3e8f-4e7e-c6b5-080d4139a008>, accessed at 2013-09-25.

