At baseline, the following self-report instruments will be administered: the Composite International Diagnostic Interview Substance Abuse Module (CIDI-SAM; cocaine and alcohol dependence; Cottler, 2000), as well as questions on suicidal risk from the MINI International Neuropsychiatric Interview (MINI; Sheehan et al., 1998); the short version of the Addiction Severity Index (ASI; McLellan et al., 1980, 1992; Hendriks et al., 1989), supplemented with questions about current illegal activities, income, and living arrangements (similar to the ASI-version used in the CRF of the Dutch RCT on medically prescribed heroin); the Time Line Follow-Back (TLFB, pertaining to cocaine use in the previous month; Sobell & Sobell, 1992); the Maudsley Addiction Profile-Health Symptoms Scale (MAP-HSS; Marsden et al., 1998); the Symptoms Check List-90 (SCL-90; Derogatis et al., 1993; Arrindel & Ettema, 1996); the Obsessive Compulsive Drug use Scale (OCDS; Anton et al., 1996; De Wildt et al., 2005), the EuroQol (EQ-5D; Brooks, 1996), and the Readiness to Change Questionnaire (RCQ; Defuentes-Merillas et al., 2002).

At the 12 weeks assessment, (follow-up versions of) each of these instruments will be administered again, with the exception of the CIDI, MINI and RCQ. In addition, patient satisfaction (Client Satisfaction Questionnaire; CSQ-8; De Wilde & Hendriks, 2005), supplemented with questions pertaining to the received medication (placebo or sustained release dexamphetamine) will be assessed.

At the 4 and 8 weeks assessment, the TLFB (pertaining to cocaine use in the previous month) and the ASI-items pertaining to other substance use will be administered, as well as the MAP-HSS, SCL-90, OCDS, and EQ-5D.

Additional assessments include blood sampling (laboratory screen: BSE, MCH, MCV, MCHC, GGT, ALAT, ASAT, alkalase phosphate, leucocytes, thrombocytes) (screening/baseline assessment and 12 weeks assessment; 2 x 16 ml), ECG (screening/baseline assessment and 12 weeks assessment), weekly medical screening; weekly check on heart rate and blood pressure during the entire study period; two times/week urine sampling (cocaine metabolites) during the 4 weeks preceding the 12 weeks assessment; monthly pregnancy testing (females); weekly registration of adverse events, serious adverse events (see: Safety reporting), and co-medication; study drug accountability (placebo and sustained release dexamphetamine); treatment compliance.

OUTCOME MEASURES AND DATA ANALYSIS

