The study data will be analyzed following an intent-to-treat (ITT) approach. The ITT-population consists of all randomized patients who received at least one dose of the prescribed medication. The end of the trial is defined as the last visit of the last patient undergoing the trial. Effect of the intervention will be evaluated in terms of potential efficacy – cocaine use (self-report; urinalyses) and craving for cocaine, use of other substances, physical and mental health, social functioning (including criminality) – as well as in terms of acceptance, medication compliance, safety, and patient satisfaction.

The primary outcome measure pertains to cocaine use, defined as the total number of days of crack-cocaine use during the 12 weeks study period (range: 0 – 84 days), and will be analyzed in a multivariate regression analysis, controlling for study group and treatment site interactions. Secondary effects of the interventions will be evaluated in terms of additional cocaine use related outcome measures (e.g., longest duration of cocaine abstinence, and the number of days cocaine abstinence as well as the mean proportion of cocaine metabolite-free urine samples in the four weeks preceding the week 12 assessment), cocaine craving, use of other substances (self-report), physical and mental health, social functioning (including criminality), and patient satisfaction. Depending on the measurement level of the secondary outcome measure, differences between the two study groups will be analyzed using 2 (time) x 2 (group) repeated measures ANOVA, multivariate (logistic) regression analyses, and GEE-modelling.

Concerning missing data, multiple imputation will be applied for missing interview data. Missing urine samples (two samples/week in weeks 9 to 12) will be considered cocaine-positive.

Since the medication will be dispensed on a daily basis and medication intake will be supervised, compliance with the study medication can be registered reliably on a daily basis. Differences between the study groups (dexamphetamine *versus* placebo) will be described and analyzed in terms of the total number of days in which the medication was taken during the 12 weeks study period, the number of consecutive weeks in which patients were fully compliant (i.e., daily medication intake), and medication intake in the four weeks preceding the week 12 assessment.

Emergency unblinding

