In the primary analysis, treatment effect will be investigated by means of a multivariate regression model with the total number of days of crack-cocaine use during the 12 weeks (84 days) study period as primary outcome measure (see above). The difference between the sustained release dexamphetamine and placebo study groups in total number of days of crack-cocaine use during 12 weeks treatment, is estimated to be 10 days, with a pooled standard deviation of 17 days (i.e., moderate effect size). Given the feasibility character of the study, the sample size should preferably be limited. As in the parallel studies of topiramate and modafinil ("New pharmacotherapeutic treatment options for crack-cocaine dependent people in the Netherlands"; NL22193.018.09; MEC09/197) we, therefore, have chosen for a lenient alpha of 0.10 to minimize loss of statistical power due to small sample size, instead of the usual 5% false-positive rate, which would be more appropriate for a future confirmatory trial. Given the two-sided alpha=0.10, and a 1-beta power of 0.80, n=36 patients are required in each study group (2x36=72 patients for the present study) (Pocock, 1983; Cohen, 1988).

SAFETY MONITORING AND REPORTING

Adverse events and adverse reactions

Adverse events (AEs) are defined as any undesirable medical experience occurring to a study subject during the study. All AEs reported spontaneously by the subject or observed by the treating physician or his staff will be registered on a weekly basis by the treating physician, defining the relationship of each AE with the study medication (definitely not, possibly, probably, certainly, unknown), and its severity. The severity of AEs will be recorded as follows:

- mild: the AE is transient and easily tolerated;
- moderate: the AE causes the subject discomfort and interrupts the subject's usual activities;
- severe: the AE causes considerable interference with the subject's usual activities and may be incapacitating or life-threatening.

All AEs will be followed until they have abated, or until a stable situation has been reached.

Adverse reactions (ARs) are defined as all undesirable responses to the study medication related to any dose administered.

Unexpected adverse reactions are adverse reactions, of which the nature or severity is not consistent with the side effects (adverse reactions) of sustained release dexamphetamine sulfate described above.

Serious adverse events and unexpected serious adverse reactions

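### The adverse event record depends on spontaneous report or staff observation, and weight is never scheduled, so some listed subjective reactions are likely to be missed in the safety comparison

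*Protocol*

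**What the plan says.** The rule for the adverse event record is in Safety Monitoring and Reporting, under Adverse events and adverse reactions: "All AEs reported spontaneously by the subject or observed by the treating physician or his staff will be registered on a weekly basis". The treating physician does the registering and grades relatedness and severity.

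The Safety profile section lists the expected reactions. Some can be measured or partly measured ("Palpitations, tachycardia, elevation of blood pressure"). Many are subjective ("overstimulation, restlessness, dizziness, insomnia, euphoria, dyskinesia, dysphoria, tremor, headache"), as are dry mouth, unpleasant taste and changed libido. It adds: "Anorexia and weight loss may occur as undesirable effects".

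Other harm-related data are scheduled. The Assessments section provides for "weekly medical screening; weekly check on heart rate and blood pressure during the entire study period", with ECG and blood tests at baseline and week 12. The Maudsley health symptoms scale (MAP-HSS), the SCL-90 and the EQ-5D are given at baseline and weeks 4, 8 and 12.

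On purpose, the background says that "the primary focus of our study will be on the balance between (potential) benefit and harm produced by the medication". The formal primary outcome is cocaine use, "defined as the total number of days of crack-cocaine use during the 12 weeks study period", and safety is one of several further terms of evaluation. The Reporting section asks for a safety analysis that weighs efficacy against harm.

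**The concern.** A rule that waits for the patient to speak, or for staff to notice, suits visible or serious events. It suits non-serious subjective ones less well. Staff cannot reliably see insomnia, palpitations, dry mouth or a change in libido, and a patient who attends every day for heroin-assisted treatment may not think such things worth mentioning. The Protocol fixes how often events are registered (weekly) but not how they are asked about.

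At stake is the adverse event comparison between arms, which feeds the benefit-harm evaluation and so the choice of a candidate medication for a confirmatory trial. This is a matter of data collection. A statistical analysis plan can decide how to summarise recorded events, but it cannot recover symptoms that nobody asked about.

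**Working it through.** **1. Which listed reactions reach the adverse event record, and how?**

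| Listed reaction | Scheduled measurement | Route into the adverse event record |
|---|---|---|
| Tachycardia, raised blood pressure | Weekly, all patients | Seen by medical staff, so can count as observed |
| Other cardiac effects | ECG at baseline and week 12 | As above, at two time points |
| Insomnia, palpitations, dysphoria, headache, dry mouth, loss of appetite, changed libido | None named; possibly some items of MAP-HSS or SCL-90 | Patient raises it unprompted |
| Weight loss | None in the text or Table 1 | Patient raises it or staff notice it |

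**2. Does the weekly check fill the gap?** Table 1 specifies the weekly medical screening as heart rate and blood pressure. Its adverse event row is marked weekly, but the only description of how events are found is the rule quoted above.

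**3. Do the symptom scales fill the gap?** Only in part.
- Table 1 places them in the researchers' block. The Assessments section describes the research assistants as independent of the treatment staff. Adverse events are in the physician's block, and no sentence passes scale answers from one to the other.
- An answer to a scale item is not a spontaneous report, so on the wording of the rule it need not be registered or graded.
- The outcome section names physical and mental health under potential efficacy, and safety separately.
- The scales are given every four weeks, so a short-lived effect may fall between them.
- Their items are not reproduced, so how far they cover the listed reactions cannot be checked.

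**4. How much could incomplete capture matter?** The documents give neither event rates nor capture fractions, so this is an illustration on assumed values. The input from the Protocol is 36 patients per arm. That figure reproduces: n = 2 × (1.645 + 0.842)² × 17² / 10² = 35.7, rounded up to 36.

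Let p1 and p0 be the true rates and c the fraction captured, equal in both arms. Expected recorded cases are 36·c·p1 and 36·c·p0, and the observed difference is c·(p1 − p0). Power uses the normal approximation at two-sided alpha 0.10, with pooled variance under the null.

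| True rates (assumed) | c (assumed) | Expected cases | Difference, points | Power |
|---|---|---|---|---|
| 30% vs 10% | 1.00 | 10.8 vs 3.6 | 20 | 0.69 |
| | 0.75 | 8.1 vs 2.7 | 15 | 0.56 |
| | 0.50 | 5.4 vs 1.8 | 10 | 0.41 |
| | 0.33 | 3.6 vs 1.2 | 6.6 | 0.30 |
| 40% vs 15% | 1.00 | 14.4 vs 5.4 | 25 | 0.78 |
| | 0.75 | 10.8 vs 4.05 | 18.75 | 0.63 |
| | 0.50 | 7.2 vs 2.7 | 12.5 | 0.46 |
| | 0.33 | 4.8 vs 1.8 | 8.25 | 0.33 |

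With counts this small the power values are rough. Equal capture leaves the ratio of rates unchanged (3 to 1 in the first set). What shrinks is the absolute difference and the chance of detecting it.

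**The case against.** The strongest reply is that harm is not measured by adverse event reports alone. Heart rate and blood pressure are taken weekly in everyone, ECG and blood tests are done twice, and structured symptom scales are given at the same visits as the cocaine interview. Physical and mental health are compared between arms, so worsening on those scales would show just as improvement would. Serious events are all to be registered, with no limit to spontaneous reports. How these sources are combined may be set out in an analysis plan that is not shown.

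All of this stands, and it rules out readings that a reader might otherwise infer: that harms are captured only passively, that expected effects are certain to be under-counted, that a low event count could not be interpreted, or that benefit is measured actively and harm passively so that the balance tilts towards the drug. The documents support none of these.

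It is also fair to say that the phrase about benefit and harm is a general background remark, that the contents of the baseline medical examination and the case report form are not itemised, and that a weekly list of stimulant effects read to patients could prompt guesses about allocation.

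The reply does not remove the narrower point. The wording of the rule is passive, no sentence links the scales to the adverse event record, and no weight measurement is scheduled.

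**Conclusion.** The point holds in a limited form. For non-serious, mainly subjective reactions, the adverse event record relies on the patient volunteering them, and one listed reaction, weight loss, has no scheduled measurement. The adverse event comparison is therefore likely to miss some expected effects. The vital signs, ECG, blood tests and symptom scales reduce the gap without closing it.

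Its size cannot be estimated from the documents. The table above rests wholly on assumed rates and on equal capture in both arms, and shows only the direction and a plausible scale. The primary analysis of cocaine use and the sample size are unaffected. This is a cheap improvement to data collection, not a flaw that invalidates the safety evaluation.

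**What to change.** 1. Amend the adverse event rule so that, at each existing weekly check, blinded staff ask every patient in both arms the same open, non-leading question about health since the last check. Spontaneous and observed events continue to be recorded as now.
2. Add weight to Table 1 at baseline and weeks 4, 8 and 12.
3. State that MAP-HSS and SCL-90 symptoms, vital signs and weight will be compared between arms as safety data alongside adverse events.

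The cost is a few minutes per visit and more minor events recorded in both arms.

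A prompted checklist of the listed reactions is optional. If one is used, flag prompted events separately from volunteered ones, and give the list at weeks 4, 8 and 12 after the cocaine-use interview, to limit any cueing of allocation guesses.

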³ Blood pressure and heart rate will be assessed weekly during the entire study period of 12 weeks.

•••• Indicates weekly (instead of monthly) registration.
